Appendix 1 : Visual Analog Scale

(Not drawn to scale)

(1 bring lowest acceptable cosmetic result, 10 being best cosmetic result)

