3.0 STUDY DESIGN

3.1 Study Design including dose escalation/cohorts/subject numbers

This is a 6 month, prospective, multicenter, double-blinded, randomized, placebo-controlled study. A total of 40 male or female healthy volunteers, 20 in each arm, will be enrolled. Up to 10 more patients can be enrolled to account for patient drop-out. Subjects will all undergo Mohs micrographic surgical removal of a skin cancer lesion on the forehead followed by reconstruction. Subjects will be randomized to receive either aboBTX-A injection or placebo injection in the frontalis, procerus, and corrugator muscles prior to reconstruction. Photographs, POSAS, and clinical assessments will be taken immediately after initial wound closure, at 1 week follow-up, at 6 weeks follow-up, and at 6 months follow-up. Adverse events will also be reviewed at each study visit. After the completion of the study, the photographs will be assessed (blinded as to the patient identifiers) using a 10 cm visual analog scale (VAS). The first few photographs will be evaluated by the surgeons together to calibrate the VAS and ensure inter-reliability.

Procedure	Visit 1: Screening & Dysport Administration	Visit 2: Op Visit	Visit 3: 1 wk f/u	Visit 4: 6 wk f/u	Visit 5: 6 month f/u
Informed Consent	X				
Pre-op Evaluation	X				
Injection of Dysport or Placebo	X				
Adverse Events	X	X	X	X	X
Medical/Medication History	X	X	X	X	X
Photography	X	X	X	X	X
Skin Evaluation		X	X	X	X
Urine Pregnancy Test	X				X
Assessments					
Physician VAS				X	X
Patient POSAS		X	X	X	X
Physician POSAS		X	X	X	X
Patient survey					X

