12.0 MEASUREMENT OF EFFECT

12.1 VAS: Visual Analog Scale. This is a 10 point scale to assess global scar assessment. At the conclusion of the study, photographs will be assessed in an independent and blinded fashion. After reviewing the photos of the wound at closure, at 6 weeks, and at 6 months, the participating raters will be asked to rate the cosmetic outcome at 6 weeks and 6 months on a 10-cm visual analog scale. The rater will be asked to assess the first patient together to establish a reference score for their respective further scores. Prior studies have shown very high intrarater consistency from VAS⁷. See statistical section for more information.

12.2 POSAS: Patient and Observer Scar Assessment Scale. The Patient and Observer Scar Assessment Scale (POSAS) consist of two numeric scales. One scale is completed by the patients, the other by the clinician. This scale is different than previous scales because it takes the patient's input into consideration. It has good internal consistency and interobserver reliability⁸⁻¹⁰. Patient POSAS will be collected at visit 2, 3, 4, and 5. Physician POSAS will be collected by each surgeon at visit 2, 3, 4, and 5. In addition, at the conclusion of the study, all four participating investigators will evaluate the photos of the wound at closure, at 6 weeks, and at 6 months for PSOAS scores in vascularity, pigmentation, thickness, and surface area. Relief and pliability will not be assessed as photographs do not allow for measurement of these values.

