14.0 STATISTICAL CONSIDERATIONS

To quantify the improvement in scar appearance, we propose the use of two well-established methods of measurement: The Visual Analogue Scale (VAS) and the Patient and Observer Scar Assessment Scale (POSAS)^{6,7}. The VAS will be used as the primary end point. It consists of a 10 point scale to assess global scar assessment. Scar photographic images are assessed by independent physicians, and previous studies have shown very high intrarater consistency. The POSAS consists of two numeric scales. One scale is completed by the patients, the other by the clinician. This scale is different than previous scales because it takes the patient's input into consideration. It has good internal consistency and interobserver reliability.^{8,9}

14.1 Visual Analog Scale: This is a 10 point scale to assess global scar assessment. VAS has been used in previous studies to assess cosmetic outcome of scars. In this study, we plan to evaluate the efficacy of using aboBTX-A to improve wound healing prior to Mohs micrographic surgery and reconstruction for skin cancer as measured by the Visual Analogue Scale (VAS) at 6 weeks post surgery as the primary endpoint.

- 14.1.1** Meaningful clinically important difference: Using the data from 2 previously published clinical trials, Quinn et al⁷ reported that the minimal clinically important difference on the VAS cosmesis scale is 1.5 on a 10 point VAS¹¹
- 14.1.2** Sample size calculation: Prior authors have reported a pooled SD of 1.4 and 2.2 among VAS scores for surgical scars, yielding an effect size (mean difference/SD) of 0.7 to 1.1. A sample size of 20 patients per treatment group would provide an 80% chance (statistical power) of detecting an effect size of 1.0, using a two-sided t-test, with a type I error level of 5%. Assuming a 5-10% dropout rate with follow-up visit and given the efficiency of the 2-sample *t* test relative to the Wilcoxon rank sum test is 95%, a total of 25 patients will be enrolled per group.
- 14.1.3** Data Analysis: The VAS ratings at 6 weeks and at 6 months for each patient will be based on the average of all four physician scores. The average of the VAS scores will then be compared between the 2 treatment groups using the Wilcoxon rank sum test. All calculated *P* values are 2-sided, and $P < 0.5$ is considered statistically significant.
- 14.1.4** Patient Accrual is anticipated that at least 10 subjects will be enrolled in the first year at UHCMC.

[figure not shown]

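### The only anchors given for the primary VAS start at the lowest acceptable result, so worse scars have no score of their own, and no rule turns a mark on the 10-cm line into a score

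*Combined protocol and SAP*

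**What the plan says.** The primary endpoint is the photographic VAS at 6 weeks, averaged over four physicians and compared between arms by the Wilcoxon rank sum test (14.1.3). The plan describes the scale in three ways:

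- **Line.** Section 12.1 has the raters "rate the cosmetic outcome at 6 weeks and 6 months on a 10-cm visual analog scale". Section 11.2 repeats this under Visit 5, and 3.1 also gives a 10-cm scale.
- **Points.** Section 14.0 says of the VAS: "It consists of a 10 point scale to assess global scar assessment". Sections 2.0, 11.2 and 12.1 use the same label.
- **Anchors.** Only Appendix 1 says what the ends mean: "1 bring lowest acceptable cosmetic result, 10 being best cosmetic result".

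For planning, 14.1.1 reports that "the minimal clinically important difference on the VAS cosmesis scale is 1.5 on a 10 point VAS", and 14.1.2 adds: "Prior authors have reported a pooled SD of 1.4 and 2.2 among VAS scores for surgical scars". Neither gives the minimum, maximum or anchors of the scales behind these figures.

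**The concern.** A scale for a primary endpoint should have a place for every outcome. Here the bottom is set at acceptable, so an unacceptable scar has no value of its own. Section 1.7 gives hypertrophic scarring as the harm that wound tension causes, so the poorest scars are those that the injection is meant to reduce. If it works, they should be commoner on placebo, and they are the ones that the form cannot tell apart.

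The observer scale in Appendix 2 does not share this gap, because its bad end is the worst scar that can be imagined.

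Three things are at stake: ties at the low end of the primary endpoint; raters who use that end differently and whose scores are then averaged; and a difference in points whose meaning against the MCID is unclear.

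**Working it through.** **1. The plan's own figures.** Effect size = MCID/SD: 1.5/2.2 = 0.68 and 1.5/1.4 = 1.07, which matches the stated 0.7 to 1.1. Exact two-sided 5% t-test power with 20 per group at effect size 1.0 is 86.9%, against the stated 80%. That miss is conservative and is a separate matter.

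**2. Width of the scale.** Anchors of 1 and 10 span 10 − 1 = 9 units; a full 10-cm line spans 10. If every score is converted by the same linear rule, ranks do not change and neither does the Wilcoxon test. Width alone therefore does no harm to the primary test. Only the floor, or raters using different rules, can.

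**3. Share of scars at the floor.** The documents give no mean VAS and no share of unacceptable scars, so the following are assumptions: on an underlying 0-10 scale, placebo mean 5, true benefit 1.5 (treated mean 6.5), SD 2.2 (the larger SD in 14.1.2), and lowest acceptable at c. The share at or below c is Φ((c − mean)/SD).

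| c | Placebo | Treated |
|---|---|---|
| 3 | Φ(−0.91) = 18% | Φ(−1.59) = 6% |
| 5 | Φ(0) = 50% | Φ(−0.68) = 25% |

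**4. Difference in means after clipping at c and at 10.** With a = (c − mean)/SD and b = (10 − mean)/SD, the clipped mean is cΦ(a) + 10(1 − Φ(b)) + mean × (Φ(b) − Φ(a)) + SD × (φ(a) − φ(b)).

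- c = 3: 6.50 − 5.21 = 1.29
- c = 5: 6.77 − 5.87 = 0.90
- placebo mean 4, c = 5: 6.13 − 5.46 = 0.67

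**5. The same differences in the form's units.** A rater who follows the form puts c at 1 and the best result at 10, so differences are multiplied by 9/(10 − c).

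- c = 3: 1.29 × 9/7 = 1.66
- c = 5: 0.90 × 9/5 = 1.62
- placebo mean 4, c = 5: 0.67 × 9/5 = 1.21

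One true benefit of 1.5 can thus be recorded as anything from about 0.7 to about 1.7, depending on where acceptable lies and on how raters spread their marks.

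**6. Wilcoxon power.** Simulated with 20 per arm, two-sided 5%, true benefit 1.5 and 6,000 runs per case:

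| Placebo mean | SD | No floor | c = 3 | c = 5 |
|---|---|---|---|---|
| 5 | 1.4 | 89.7% | 88.8% | 87.0% |
| 5 | 2.2 | 54.0% | 52.3% | 49.2% |
| 4 | 1.4 | 89% | – | 81% |
| 4 | 2.2 | 53% | – | 45% |

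Simulation error is up to about √(0.5 × 0.5/6,000) = 0.6 points per figure. Over placebo means of 4 to 6 and cut points of 1 to 5, the loss is about 0 to 10 points, mostly under 5. The floor is applied to each patient's score as a whole. If the four raters differ on where acceptable begins, their averages will have fewer exact ties than this, but will mix different scales.

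**The case against.** The strongest reply is that this is wording on a form and that the analysis is protected. The test uses ranks, raters are blinded, four scores are averaged, and calibration is planned on the first few photographs (3.1) or the first patient (11.2, 12.1). A floor shared by both arms under blinding does not favour the active arm. Section 4.2 excludes patients with a history of keloid or hypertrophic scarring, which should make unacceptable results rarer. The drawing in Appendix 1 is not visible in the text and is marked as not to scale, so the printed line might start at 0.

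Much of this stands. It is why the power loss is small and why a false positive is not the worry. It does not supply what is missing. Calibrating on one patient gives a reference score but does not define the low end, and the caption remains the only anchor wording in the plan.

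Two stronger readings are tempting. A reader might infer that the MCID belongs to a 0-10 line and should be cut to 1.5 × 9/10 = 1.35 here. The documents do not support that: 14.1 calls both the trial's scale and the MCID's scale 10-point, and gives no range for the source. If MCID and SDs rescaled together, the effect sizes would not move in any case. A reader might also infer that the floor must shrink the difference between arms. It does so in 0-10 units (step 4), but in the form's own units it can come out above or below 1.5 (step 5).

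**Conclusion.** The point holds at low severity. The described instrument (a 10-cm line) and the supplied anchors (1 as lowest acceptable, 10 as best) do not match, scars below acceptable have no defined score, and no conversion from mark to score is given.

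The cost to the primary test is at most a few points of power under most assumed distributions, reaching 8 points in the tabulated cases only when the assumed cut point lies above the placebo mean. The cost to interpretation is larger: the observed difference is distorted in a direction that cannot be predicted, and the plan does not show that the 1.5 MCID or the SDs of 1.4 and 2.2 apply to a scale anchored this way. The means and cut points are assumptions; the SDs, the MCID, 20 per arm and the 5% level come from 14.1.

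**What to change.** Before the photographs are rated at the end of the study:

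1. Make Appendix 1 a single 100-mm line, anchored 0 = worst possible scar and 10 = best possible cosmetic result, scored by measured distance from the low end (millimetres divided by 10).
2. Use the same range and anchors in 2.0, 3.1, 11.2, 12.1 and 14.1.
3. State in 14.1.1 that applying the 1.5 MCID assumes a source scale with the same range and anchors. Re-anchoring the form does not by itself establish this; it has to be checked against the source.

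The cost is one edited form and a few matching sentences. VAS ratings are made from stored photographs at study end, so no visit or patient is affected. Once ratings have been made on the present form, ties at the floor can be undone only by rating again.

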Appendix 2: Patient and Observer Scar Assessment Scale

Table IV. The Patient and Observer Scar Assessment Scale.*

	Normal skin	Observer Scar Assessment Scale (OSAS)										Worst scar imaginable
		1	2	3	4	5	6	7	8	9	10	
Vascularity		0	0	0	0	0	0	0	0	0	0	
Pale												
Pink												
Red												
Purple												
Mix												
Pigmentation		0	0	0	0	0	0	0	0	0	0	
Hypo												
Hyper												
Mix												
Thickness		0	0	0	0	0	0	0	0	0	0	
Thicker												
Thinner												
Relief		0	0	0	0	0	0	0	0	0	0	
More relief												
Less relief												
Mix												
Pliability		0	0	0	0	0	0	0	0	0	0	
Supple												
Stiff												
Mix												
Surface area		0	0	0	0	0	0	0	0	0	0	
Expansion												
Contraction												
Mix												
Overall opinion		0	0	0	0	0	0	0	0	0	0	
		Patient Scar Assessment Scale (PSAS)										
	No, not at all	1	2	3	4	5	6	7	8	9	10	Yes, very much
Has the scar been painful the past few weeks?		0	0	0	0	0	0	0	0	0	0	
Has the scar been itching the past few weeks?		0	0	0	0	0	0	0	0	0	0	
	No, as normal skin	1	2	3	4	5	6	7	8	9	10	Yes, very different
Is the scar colour different from the colour of your normal skin at present?		0	0	0	0	0	0	0	0	0	0	
Is the stiffness of the scar different from your normal skin at present?		0	0	0	0	0	0	0	0	0	0	
Is the thickness of the scar different from your normal skin at present?		0	0	0	0	0	0	0	0	0	0	
Is the scar more irregular than your normal skin at present?		0	0	0	0	0	0	0	0	0	0	
	As normal skin	1	2	3	4	5	6	7	8	9	10	Very different
What is your overall opinion of the scar compared to normal skin?		0	0	0	0	0	0	0	0	0	0	

Appendix 3: Patient Satisfaction Questionnaire

1. Please rate how satisfied you are with the result of scar (wound?):

1: Excellent 2: Very good 3: Good 4: Fair 5: Poor

2. Would you recommend using Dysport (botulinum toxin A) to help reduce scarring?

1: Yes 2: No

Appendix 4: Dysport Prescribing Information
